- * Following in depth discussion with the Research Ethics Committee, it was decided that, since some of the outcome questionnaires had not been validated in languages other than English, we should exclude from the study people who do not understand written or spoken English.

Interventions

Participants will receive PTNS or sham using the recommended standard of 12 weekly 30 minute outpatient stimulations [Figure 1]. The stimulation protocol is based on that currently recommended by the manufacturer, NICE guidelines and used by most centres treating urinary disorders (including OAB SUMMIT trial) and FI [41].

The sham arm will use a modification of that used in the pivotal level I trial of Peters *et al.*, [41] in overactive bladder syndrome and previously validated by this group [52]. The main difference is that the sham proposed in the current study improves on that used by Peters by actually inserting (at the same

site) the Urgent ® PC needle in all subjects. In the Peters study, the Urgent PC ® needle was used in the PTNS arm, but the sham employed an acupuncture technique using a Streitburger needle, which does not puncture the skin. (A legitimate concern regarding sham validity).

In the CONFIDeNT study, all participants will have a PTNS machine and a TENS machine set up on their RIGHT foot, as shown below. (Unless there is a reason why the right foot cannot be used, in which case this should be documented). In the true PTNS arm, the PTNS machine will be utilised as normal, and the TENS machine left turned off. In the sham arm, the Urgent PC ® needle will be placed subcutaneously, and not connected to the machine, and the electrical stimulation delivered to the distal foot using TENS. All subjects have a needle and 3 surface electrode pads placed as shown in figure 3 (A, B & C) to standardize the perception of the intervention between the 2 arms. Electrode A is used for the treatment and B & C for the sham. See Appendix 2.

This sham has been shown in a departmental pilot to be both more acceptable and more realistic than that described by Peters et al, involving placement of a Streitberger needle. We have also confirmed that this sham, using TENS to deliver the electrical stimulation, does not stimulate the posterior tibial nerve (proven in a neurophysiological pilot by Consultant Neurophysiologist). Further, it has been trialled successfully at both road show meetings and is easily learnt.

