Figure 2: Images of percutaneous tibial nerve stimulation

Needle in place at left ankle attached to portable stimulator unit (urgent PC ®)

[figure not shown]
Patient undergoing outpatient stimulation

Treatment arm: This uses the Urgent ® PC neuromodulation system (Uroplasty Ltd., Manchester, UK) [39-41]. After checking equipment including battery level, the site of insertion is identified at a location on the lower inner aspect of the RIGHT leg approximately three finger breaths (5 cm) cephalad to the medial malleolus and approximately one fingerbreadth (2 cm) posterior to the tibia. The area is cleaned with ethanol and the needle electrode-guide tube assembly placed over the identified insertion site at a 60-degree angle between electrode and ankle. The 34 gauge needle electrode is gently tapped to pierce the skin and thence advanced using a rotating motion approximately 2cm. The lead wire is then connected to the stimulator and to the ipsilateral calcaneal reference electrode (A. in figure 3) (as standard practice). The lead wire is then taped to the participants leg in order that the PTNS participant will experience the same sensations as the sham participant (see below). The inactive electrodes (B & C) are attached as shown and connected to the TENS machine (Biostim M7 TENS unit, Biomedical Life Systems, Vista, California). The TENS machine is not turned on.

The PTNS stimulator is a reusable external pulse generator that provides visual and auditory feedback. It has an adjustable current setting from 0-9mA in preset 0.5 mA increments, a fixed-pulse frequency of 20Hz and a pulse width of 200 microseconds. After determining the setting for therapy by increasing the current slowly whilst observing the participant's sensory or foot for toe / ankle extensor motor responses, the current is reduced by one level for therapy. Therapy is continued for 30mins and thence the electrode removed. Treatment is repeated for 12 sessions within the three-month duration exact intervals tailored to participant's needs but must comply with study requirements: Requirements – 12 treatments within 13 weeks, no two treatments less than 5 days or greater than 10 days apart). Side effects include occasional tenderness at the site of needle insertion [39,40].

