Sham arm: the same protocol is followed as above. The only difference is that the needle will be inserted only 2mm into the skin and subcutaneous tissue i.e. just in far enough to not fall out and not deep enough to be close to the posterior tibial nerve. The lead will then be taped to the participants leg near to, but not touching the needle. The purpose of this is to prevent unbinding in the event of the participant inadvertently seeing the equipment. The PTNS surface electrode (A) on the calcaneous is also attached as above. The two active TENS surface electrodes (B & C) are employed as demonstrated below, with one under the little toe and one on top of the foot. Once all equipment is set up, the practitioner picks up both the Urgent PC machine and the TENS machine, one in each hand. Both machines are turned on. The TENS machine should be set to a pulse frequency of 10Hz and a pulse width of 200 microseconds. Then, pressing buttons simultaneously on the Urgent PC and the TENS machine, the practitioner should increase the adjustable current setting (which ranges from 0-10mA in preset 1mA increments on the TENS machine) and in the usual way determine the setting for therapy by observing the participant's sensory or foot for toe / ankle extensor motor responses, the current is reduced by one level for therapy. The reason both machines are picked up together is so that the audible sounds produced by the Urgent PC stimulator are the same in both the PTNS and sham arms, to decrease auditory variation between the study arms.

Figure 3: PTNS needle and surface electrode (A). TENS surface electrode placements (B & C). Note: The PTNS and TENS electrodes are inserted / connected on all subjects identically.

Randomisation

Participants will be randomised, with allocation concealment, at visit 2 using a web-based computer program to receive either PTNS or sham. This will be performed using a bespoke programme designed and held at the Nottingham Clinical Trials Unit. Study centres will input the unique participant identifier and gender of the participant and immediate on-screen randomisation will occur. This information should immediately be recorded on CRF 4 (randomisation information), which is stored separately from the other CRFs.

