Stratification will occur in the following way; strata 1 = men; then women will be stratified by centre. Stratification by gender will be used to reduce the potential confounding effects of variation in outcomes between male and female participants. Males represent approximately 10% of patients and have differing pelvic physiology and often disease aetiology (e.g. post anal surgery rather than childbirth). As only 1 or 2 male participants are expected to be enrolled from each centre, randomisation stratified on centre would allow the possibility that all the males are allocated to PTNS by chance. To avoid this scenario, we will therefore only stratify women by centre, so achieving near balance of PTNS and sham arms and ensuring comparability by centre.

Allocation concealment

Blinding of participants: For both interventions: (1) a standardised description of the techniques will be read from a card (See Appendix 2). This will describe an electrical sensation variably in the ankle or foot with or without motor responses in the foot (note: there is significant variability in conscious sensation and motor responses even between participants undergoing only PTNS); (2) the lower extremity will be draped from view; and (3) the audible sounds produced by the Urgent PC unit will be identical.

Performance bias considerations: Since the sham group might be expected to seek more advice than the treatment arm (if the hypothesis that PTNS is more effective than placebo is correct), the interaction of the administering nurse / physician will be standardised so that general supportive advice given at consultations is identical for all participants. This will be limited to a general welcome, answers to any concerns (whilst recording adverse events), advice on loperamide dosages and pad use (both recorded in outcome variables).

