Appendix 1: Study Centre Codes

[figure not shown]
Aintree University Hospitals NHS Foundation Trust	ANT
Barts and the London NHS Trust	BLT
United Hospitals Bristol NHS Foundation Trust - Bristol Royal Infirmary	BRI
University Hospital of North Durham	CDD
Hull and East Yorkshire Hospitals NHS Trust - Castle Hill Hospital	CHH
Homerton University NHS Foundation Trust	HNT
South London Healthcare NHS Trust - Queen Elizabeth Hospital, Woolwich	QEH
Nottingham University Hospitals NHS Trust - Queen's Medical Centre	QMC
St Marks Hospital, Northwick Park	SMH
Salford Royal NHS Foundation Trust, Manchester	SRH
Sheffield Teaching Hospitals NHS Foundation Trust	STH
Sandwell and West Birmingham NHS Trust	SWB
University College London Hospitals	UCL
University Hospitals of Leicester - Leicester General Infirmary	LGI
University Hospital Southampton NHS Foundation Trust	SOT
Whipps Cross University Hospital, London	WCU
University Hospital of South Manchester, Wythenshawe Hospital	USM
University Lincolnshire Hospital Trust - Pilgrim Hospital	ULH
Glan Clywd Hospital, Rhyl	GCH
Guy's and St Thomas' Hospital NHS Trust	GST
Leeds Teaching Hospitals NHS Trust - Leeds Royal Infirmary	LRI
Mid Yorkshire Hospitals NHS Trust	MYH
Northern Lincolnshire & Goole Hospitals NHS Trust	NLG
Rotherham Hospital NHS Foundation Trust	RHT
The Royal Liverpool and Broadgreen University Hospitals NHS Trust	RLU
Taunton & Somerset NHS Trust	TST
Poole NHS Foundation Trust	PHT

CONtrol of Faecal Incontinence using **D**istal **N**euromodula**T**ion (CONFIDeNT)

Standardised PTNS and Sham

[figure not shown]
EQUIPMENT SET UP

Figure 1

- Just distal to calcaneus on sole of foot in midline (active for PTNS)
- 2. Bottom of foot just proximal to smallest toe
- 3. Top of foot just above smallest toe

Figure 2

PTNS: Urgent ® PC neuromodulation system (Uroplasty Ltd., Manchester, UK).

- Needle: Lower inner aspect of the RIGHT leg three finger breaths (5 cm) cephalad to the medial malleolus and approximately one fingerbreadth (2 cm) posterior to the tibia. 60-degree angle between electrode and ankle.
- Electrode: Ipsilateral calcaneus.

TENS: Biostim M7 TENS unit, Biomedical Life Systems, Vista, California

• Electrodes: Right foot, one under the little toe and one on top of the foot.

FOR PTNS:

- Set up both machines.
- Place tape over wire connected to PTNS needle (so appearance is identical to sham).
- Only turn on PTNS machine fixed-pulse frequency of 20Hz and a pulse width of 200 microseconds

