- Continue treatment as usual increasing amplitude until a sensory or motor response reduce.
- DO NOT ALLOW PARTICIPANT TO ALTER SETTINGS THEMSELVES

FOR SHAM:

- Set up both machines. With PTNS, DO NOT CONNECT LEAD TO PTNS NEEDLE.
- Instead, tape lead near needle so it is not possible to tell at a glance if connected or not.
- Pick up both the TENS and PTNS machines
- Check TENS settings pulse frequency 10Hz and pulse width 200 microseconds.
- Press buttons simultaneously on PTNS and TENS machines to increase Amplitude (participant will only fell TENS as PTNS machine is not properly connected). THE PARTICIPANT WILL THEN HEAR THE BEEPS FROM THE PTNS MACHINE AS IN THE PTNS ARM.
- When a significant sensory of motor response is observed, turn down one setting.
- Press timer button twice 30 mins will count down on TENS display
- Leave the participant as usual for the 30 minute treatment.
- DO NOT ALLOW PARTICIPANT TO ALTER SETTINGS THEMSELVES

VERBAL EXPLANATION TO PARTICIPANT

"I am now going to start the nerve stimulation treatment. I will be inserting a small electrode needle, like an acupuncture needle, into your leg and putting sticky electrodes onto your foot. When I turn the machine you will be asked when you can first feel an electrical sensation in your ankle or foot. Occasionally you may also feel numbness or slight movement of your toes. This is normal. I will set the machine up and leave it running for 30 minutes. You may or may not continue to feel the stimulation during this time – this is normal also. After 30 minutes have elapsed I will remove the needle and sticky electrodes (the machine automatically turns off at this time). If the treatment becomes uncomfortable at any point please let me know and I will turn it down or stop the machine."

References

- 1. Nelson RL. Epidemiology of fecal incontinence. Gastroenterology 2004; 126 (suppl 1):S3-S7.

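### The two arms are given different machine-handling steps, only sound is matched, and nothing says the machines are out of the participant's view

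*Protocol*

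**What the plan says.** The Interventions section and Appendix 2 (Standardised PTNS and Sham) set out operator steps for each arm.

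For sham, the Sham arm paragraph states that "the practitioner picks up both the Urgent PC machine and the TENS machine, one in each hand", and then "Both machines are turned on". Appendix 2, under its sham list, adds "Press buttons simultaneously on PTNS and TENS machines to increase Amplitude" and "Press timer button twice 30 mins will count down on TENS display".

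For PTNS, the Interventions overview says that "the PTNS machine will be utilised as normal, and the TENS machine left turned off". The Treatment arm paragraph repeats it: "The TENS machine is not turned on". Appendix 2, under its PTNS list, has "Only turn on PTNS machine".

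The Sham arm paragraph opens by saying that the treatment-arm procedure is followed and that shallow needle insertion is all that sets sham apart. It later explains that both machines are lifted together so that the Urgent PC sounds alike in both arms.

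The participant-blinding text under Allocation concealment lists three measures: a standard description read from a card, the drape ("the lower extremity will be draped from view"), and identical sounds from the Urgent PC.

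**The concern.** The arms are matched for pads, needle site, taping and sound, but not for what the operator does with the two machines. If a participant sees this, it is a feature of the session that depends on allocation.

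Participant blinding carries most of the protection in this trial. The primary outcome comes from a diary that the participant fills in, and an episode counts if the participant thinks it worth entering. The incontinence score, quality-of-life measures and global impression are also self-rated. The Background stresses that placebo responses in this field are large. A difference in expectation between arms could therefore reach the primary comparison directly.

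**Working it through.** No figure in the protocol depends on this point, so there is nothing to recompute. The sample size of 212 is not affected. The check is a comparison of the instructions.

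| Operator step | Sham | PTNS |
|---|---|---|
| Both units attached to the participant | Yes | Yes |
| Lead or wire taped for appearance | Yes | Yes |
| Both units picked up, one in each hand | Yes (Sham arm; Appendix 2) | No such step |
| TENS unit switched on | Yes (Sham arm) | No (overview; Treatment arm; Appendix 2) |
| Buttons on both units pressed together | Yes (Sham arm; Appendix 2) | No such step |
| Countdown started on the TENS display | Yes (Appendix 2) | No such step |

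1. **Do the arms differ as written?** Yes, in the last four rows. The PTNS steps contain nothing that mirrors them.

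2. **Does this conflict with another statement?** Yes. The Sham arm paragraph names needle depth as the single departure from the treatment-arm procedure and then describes several more.

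3. **Is the difference covered by a stated safeguard?** The drape is described for the lower leg only. The sound measure deals with sound. The card is the same for both arms but does not change what is done. No section says where the units are held or placed, which way the displays face, or that the operator's hands are screened.

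4. **Does the protocol itself treat appearance as relevant to blinding?** Yes. Appendix 2 has the PTNS wire taped so that it looks like sham, and the Sham arm paragraph has the lead taped in case the participant happens to see the equipment. The Treatment arm paragraph notes that the stimulator gives visual as well as auditory feedback. That reasoning was applied to the tape but not to the handling or the displays.

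5. **How often does the instruction apply?** At each of 12 scheduled sessions for the 106 planned sham participants. This counts a written instruction, not cues that were seen.

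**The case against.** The strongest reply is that a difference in procedure is not a failure of blinding. Much of it stands.

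- **Visibility.** A reader might infer that sham participants see the two-machine handling at all 12 sessions. The protocol does not say so. It gives no layout, treats sight of the equipment as accidental, and its set-up figures are not available here. What can be said is that the handling could be seen and that no screening is stated.
- **Interpretation.** Both machines are attached in both arms, people with previous PTNS or SNS are excluded, and each participant experiences one procedure. They have no reference for normal handling.
- **Direction.** A reader might infer that any bias favours PTNS. That would need sham participants to guess correctly. A naive participant could equally take two working machines as the fuller treatment, or one machine left off as the lesser. The direction cannot be derived.
- **Standardised perception.** A reader might set the handling against the overview's aim of standardising perception. That sentence concerns the needle and three pads, which are matched. The real conflict is with the single-difference statement.
- **Script.** The card speaks of one machine, but it is read in both arms and both have two units attached, so it identifies neither.
- **Perceived allocation.** The question at the final visit is not weakened by such a cue. It could reveal a blinding failure, although too late to prevent one.
- **Pilot.** The overview reports that a departmental pilot found this sham more realistic than the earlier one. No data are given, and the text does not say that machine handling was assessed.

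None of this explains why the handling is left unmatched, or supplies the missing statement about view.

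**Conclusion.** The point holds in a limited form. The handling steps differ by arm as written, they contradict the statement that needle depth is the only difference, and the stated safeguards do not cover what the participant may see of the machines or the operator. Participants could therefore see arm-specific handling at any session of a trial whose main outcomes are self-reported.

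The size is unknown. The share who would notice, the share who would infer their arm, and the sign and amount of any bias cannot be obtained from the protocol. The conclusion rests on the written instructions and assumes that sites follow them as they stand. It does not show that blinding fails. This is an inexpensive improvement, not a flaw that undermines the design.

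**What to change.** Reconcile the Interventions overview, the Treatment arm and Sham arm paragraphs, the participant-blinding text under Allocation concealment, and both lists in Appendix 2, so that:

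1. In both arms the two units, their displays and the operator's hands are kept out of the participant's sight throughout, for example by extending the drape.
2. Both units are picked up in both arms. In the PTNS arm no button on the TENS unit is pressed, because it is connected to the participant and mimicked presses could switch it on.
3. The statement that needle depth is the only difference is replaced by a correct list of the differences.

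The stimulation delivered in either arm does not change. The cost is a short edit, a site notice, and a few seconds of handling per session.

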Visit 3-13: intervention – interim information: At appointments 3-13, a member of the local team (which may be the same member as in Visit 2) will deliver the 30 minute intervention. They will check on CRF 4, prior to commencement, to make sure of the randomisation allocation, either PTNS or sham.

During this appointment with the participant, the researcher will enquire about adverse events, concomitant medication usage and pad usage, and record these on CRF 5.

At Visit 7, participants will be given a one week interim bowel diary to fill in between Visits 7 and 8. This bowel diary will then be collected and checked at Visit 8. Intervention parameters will also be entered on CRF 5.

At Visit 13, participants will also be given a two week bowel diary and CRF 3 questionnaire document to complete prior to attending Visit 14, two weeks later.

Visit 14: final study visit: The final study visit will be performed by a blinded member of the research team (i.e. somebody who has not been present at visits 2-13).

At this appointment, the bowel diary and CRF 3 questionnaire document will be collected and checked for completeness. The participant will then be asked to complete CRF 6, the post treatment questionnaire.

The research member will then ensure all documents are present and filled in correctly, and then ask the PI to complete and sign CRF 7. Once this has all been completed, the participant can be unblinded as to their treatment allocation if they wish. This is the final study visit, so further follow up should be arranged at this visit.

If participants have failed to complete the Interim Bowel Diary between Visits 7 and 8, this should be attempted again the following week. This is a Protocol Deviation, and therefore a 'Note to File CRF' should be completed to explain this. If participants fail to complete the Final Bowel Diary, again this should be attempted again after Visit 14, and participants brought back to collect this. This is also a Protocol Deviation, and should be documented in a 'Note to File CRF'.

After completion of trial: After Visit 14, participants who received 'sham' stimulation will be offered PTNS at this time, if they wish.

Participants who received real PTNS who derived significant benefit, will be offered 'top-up' sessions on an ad hoc basis, and will be followed up in NHS clinics in the usual way.

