Participants who received real PTNS who derived no significant benefit will be offered further treatments on an 'open-label' basis, following local step-wise management protocols.

Table 2: Events at each visit

Event	Visit 1	Telephone Conversation	Visit 2	Visits 3-13	Visit 14
Eligibility assessment	Χ				
Bowel Diary		X		Visit 7-8	Х
Consent			Χ		
Participant Contact Information Sheet			Χ		
Eligibility assessment (CRF1)			Χ		
Initial assessment (CRF2)			Χ		
Questionnaires (CRF3)			Χ		Х
Randomisation			Χ		
Randomisation information (CRF4)			Χ		
Intervention			Χ	X	
Record stimulation parameters adverse events and medication / pad usage (CRF5)			Х	Х	
Adverse Events Log			Χ	Х	Х
Concomitant Medications Log			Χ	X	Х
Post treatment Information (CRF6)					Х
Final Study Visit Information (CRF7)					Х

Inclusion and exclusion criteria

Broadly, eligibility will be failure of appropriate conservative therapies in patients with symptoms that are sufficiently severe to warrant intervention. It is expected that many patients will have had NICE-recommended appropriate specialist investigations including structural and functional anorectal assessment although these are not mandatory. Anal sphincter injury is not a contra-indication [32].

Inclusion Criteria

- Faecal incontinence sufficiently severe enough to warrant intervention
- Failure of appropriate conservative therapies
- Age ≥ 18 years

Exclusion Criteria

- Inability to provide informed consent for the research study
- Inability to fill in the detailed bowel diaries required for outcome assessments (this will exclude participants who do not speak / read English)*
- Neurological diseases, such as diabetic neuropathy, multiple sclerosis and Parkinson's disease (any participant with painful peripheral neuropathy)
- · Anatomical limitations that would prevent successful placement of needle electrode
- Other medical conditions precluding stimulation: e.g. bleeding disorders, certain cardiac pacemakers, peripheral vascular disease or ulcer, lower leg cellulitis
- Congenital anorectal anomalies or absence of native rectum due to surgery
- A cloacal defect
- Present evidence of external full thickness rectal prolapse
- Previous rectal surgery (rectopexy / resection) done < 12 months ago (24 months for cancer),
- Stoma in situ
- Chronic bowel diseases such as inflammatory bowel disease leading to chronic uncontrolled diarrhoea
- Pregnancy or intention to become pregnant
- Previous experience of SNS or PTNS

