An AE is any untoward medical occurrence in a participant to whom an intervention has been performed, including occurrences which are not necessarily caused by or related to that intervention. An AE can therefore be any unfavourable and unintended sign, symptom or disease temporarily associated with study activities.

The PTNS treatment and placebo have no recognised significant adverse effects. However, at each weekly visit each participant will be asked if they have had any new symptoms or medical conditions since their last visit. This will be documented on CRF 5. If any Aes have occurred, the AE will be recorded on the AE Log.

Serious Adverse Events are defined as follows:

- Fatal results in death (NOTE: death is an outcome, not an event)
- Life-threatening
- Requires inpatient hospitalisation or prolongation of existing hospitalisation
- Results in persistent or significant disability/incapacity
- Is a congenital anomaly/birth defect

Investigators Assessment

Seriousness

The Chief/Principal Investigator responsible for the care of the participant, or in his absence an authorised medic within the research team, is responsible for assessing whether the event is serious according to the definitions given above.

Causality

The Investigator must assess the causality of all serious adverse events in relation to the trial treatment according to the definition given.

Expectedness

The investigator must assess the expectedness of all SAEs according to the definition given. If the SAE is unexpected and related, then it needs reporting.

Severity

The Investigator must assess the severity of the event according to the following terms and assessments. The intensity of an event should not be confused with the term "serious" which is a regulatory definition based on participant/event outcome criteria.

- Mild: Some discomfort noted but without disruption of daily life
- Moderate: Discomfort enough to affect/reduce normal activity
- Severe: Complete inability to perform daily activities and lead a normal life

Reporting

If the event is classified as SERIOUS, the CI will be informed immediately, and will report all SAEs that are RELATED to the study and are UNEXPECTED to the main research ethics committee (REC) using the NRES non-trials SAE form and SOP within 15 days of the CI being made aware of the event.

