Identifiable data will be recorded on the Participant Contact Information Sheet. This will be stored with the Participant Consent Form in the 'Consent Form Folder', separately from the other CRFs. All other CRFs will contain no identifiable data, but will contain Unique Participant Identifier (as detailed above), so can be stored together in the CRF Folder for each individual. All Randomisation Information CRFs (CRF 4), should be kept separately from the other CRFs, in the 'Randomisation Folder' containing CRF 4s for all

participants at that centre. This folder can thus be referred to prior to each treatment, but it will not be stored with the other CRFs to prevent inadvertent unblinding.

The following Case Report Forms are to be completed:

- CRF 1: Eligibility Assessment to be completed by research member prior to randomisation
- CRF 2: Initial Assessment - to be completed by research member prior to randomisation
- CRF 3: Questionnaires to be completed by participant prior to randomisation (with help from research member as required)

GI Quality of Life Index
Patient Centred Outcomes Form
SF-36
Quality of Life Scale for Faecal Incontinence
Cleveland Clinic Faecal Incontinence Score
EQ -5D Health Questionnaire

- CRF 4: Randomisation Information to be completed by unblinded researcher
- CRF 5: Documentation for Visits 2-13 to be completed by unblinded researcher
- CRF 6: Post Treatment Information to be completed by blinded researcher and participant
- CRF 7: Final Study Visit Information to be completed by PI

Additional CRFs: - all to be completed by research member

Adverse Events Log
Concomitant Medications Log
Early Withdrawal from Study
Serious Adverse Event form
Screen Failure CRF
Unscheduled Visit CRF
Note to File CRF

Other Information Recorded

Bowel Diary: Each participant will also complete a 2 week bowel diary prior to commencement of the treatment and following treatment and a 1 week bowel diary between visits 7 and 8. This is not outside normal NHS practice, and this information will be analysed alongside trial data.

Participant Contact Information Sheet: Each participant will provide personal details, contact details and GP details. This will be the only identifiable data kept on each participant, and will be kept separately from the non-identifiable CRFs.

Transport of Trial Data

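### The only worded adverse event question does not ask about worsening, although the protocol's own definition covers it, and the protocol does not say how events are elicited at Visit 14

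*Protocol*

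**What the plan says.** **Definition.** The Adverse events section of the protocol states: "An AE can therefore be any unfavourable and unintended sign, symptom or disease temporarily associated with study activities". Nothing in it confines an AE to something that began after enrolment.

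**Question.** The next paragraph of that section says that "at each weekly visit each participant will be asked if they have had any new symptoms or medical conditions since their last visit". It continues: "This will be documented on CRF 5. If any Aes have occurred, the AE will be recorded on the AE Log". This is the only place where the protocol gives the content of the question.

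**Treatment visits.** Under Events at each visit, the entry for Visits 3-13 says that "the researcher will enquire about adverse events, concomitant medication usage and pad usage, and record these on CRF 5".

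**Form and completer.** The Case Report Forms section lists "CRF 5: Documentation for Visits 2-13 to be completed by unblinded researcher".

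**Final visit.** Visit 14 takes place two weeks after Visit 13 and is run by a team member who is blinded to allocation. Its description covers collecting and checking the diary and the CRF 3 questionnaires, then "The participant will then be asked to complete CRF 6, the post treatment questionnaire", then sign-off of CRF 7 by the local principal investigator. After that the participant may be told the allocation. No AE enquiry is described. Table 2 nevertheless marks the "Adverse Events Log" at Visit 14 as well as at the treatment visits, and the list of other recorded variables under Trial outcomes says AEs are recorded at every visit.

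**The concern.** Two things do not line up.

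First, the scripted question is narrower than the definition it is meant to serve. Everyone enrolled already has faecal incontinence, and the protocol notes that many such patients also have urinary symptoms. An aggravation of an existing complaint is therefore a foreseeable kind of harm in this population. It falls within the definition, but a participant could truthfully answer no to a question about new symptoms or conditions.

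Second, the question is attached to the weekly visits and to a form that stops at Visit 13. The final visit, which is the one run by a blinded assessor, has an AE Log to fill but no stated means of filling it.

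What is at stake is the completeness and consistency of the harm data in both arms. If sites read the text differently, some will ask about worsening and about the two weeks after treatment and others will not. In the treatment period, the person asking and recording knows the allocation, so any latitude in how the question is put is exercised by someone who is not blinded.

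**Working it through.** No arithmetic applies. The protocol states no expected AE rate, so there is no figure to reproduce and none from which to estimate missed events. The check is a comparison of the sections.

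1. **Definition against question.** The definition turns on "any unfavourable and unintended sign, symptom or disease", with no condition on when it started. The question turns on newness. Even if *new* is read as qualifying only symptoms and not medical conditions, the sentence still does not mention an existing problem getting worse. The question is a strict subset of the definition.

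2. **Does another sentence close the gap?** The Visits 3-13 entry has the researcher enquire about AEs in general. That is broader, but it gives no wording and its answers go on the same CRF 5. A site looking for what to ask would find only the sentence in the Adverse events section.

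3. **Is worsening captured elsewhere?** In part. Bowel diaries are kept at baseline, between Visits 7 and 8, and over the two weeks before Visit 14. The Cleveland Clinic Score and a short urinary assessment are secondary outcomes. Pad and medication use are asked about at Visits 3-13. These are outcome or covariate data, however, and do not by themselves produce an AE Log entry with an assessment of seriousness and severity. The Clinical outcomes text also says that participants who withdraw before the final visit will have no secondary outcome data.

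4. **Who asks during treatment.** CRF 5 is completed by the unblinded researcher at Visits 2-13. The Blinding of trial staff paragraph says that the same researcher normally gives all 12 treatments. The enquiry in this period is therefore made by staff who know the allocation. The participants answering are blinded by draping, a standard script and matched sounds.

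5. **What happens at Visit 14.**

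| Place in the protocol | AE activity at Visit 14 |
|---|---|
| Table 2, AE Log row | Marked |
| Table 2, CRF 5 row (includes AEs) | Blank |
| Trial outcomes, Other recorded variables | Recording at every visit |
| Adverse events section | Question tied to weekly visits and CRF 5 |
| Events at each visit, Visit 14 | Diary, CRF 3, CRF 6, CRF 7; no AE enquiry described |
| Case Report Forms list | CRF 5 ends at Visit 13 |

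Recording at Visit 14 is scheduled, but the means of eliciting events is not stated. Visit 14 comes two weeks after Visit 13, so the weekly question does not plainly extend to it. The item content of CRF 6 and CRF 7 is not shown, so an AE item on either cannot be ruled out.

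**The case against.** The strongest reply is that this is a matter of form wording and that the protocol's intent is clear. The definition is broad, the researcher is told to enquire about AEs at Visits 3-13, and AEs are to be recorded at every visit. CRF 5 is a treatment-session form, so its absence from a visit without treatment is expected. Worsening incontinence and urinary symptoms are measured as outcomes. New leg pain from a needle would be a new symptom and so would be caught by the question as it stands. Most of this is fair, and it limits the size of the point. It does not remove the mismatch between the definition and the only question that is spelled out.

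The same facts rule out several stronger conclusions that a reader might draw.

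- **That events after the last treatment are not solicited.** Table 2 schedules the AE Log at Visit 14, recording is promised at every visit, and CRF 6 or CRF 7 may hold an item. The text supports only that the method is not stated.
- **That harms have no blinded ascertainment.** Participants, who report the events, are blinded, and Visit 14 is run by a blinded team member. Having an unblinded operator is hard to avoid with a needle device, and the protocol responds by standardising the operator's interaction across arms.
- **That a few missed events would change the safety conclusion.** AEs are listed among other recorded variables, not as a primary or secondary outcome, and the protocol's analysis section names no between-arm harm test. Nothing in it supports an estimate of how many events would be missed.

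**Conclusion.** The point holds in a limited form. The worded AE question is narrower than the protocol's own definition because it omits worsening. It sits on a form completed by unblinded staff that ends at Visit 13. For Visit 14, AE recording is scheduled without any statement of how events since the last treatment are to be elicited. The Visit 14 element alone is mainly a matter of bringing the sections into line with Table 2.

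The effect on AE counts cannot be quantified from the protocol. The share of follow-up falling after the last treatment does not measure missed events, because it presumes that nobody asks at Visit 14. The upper confidence bound for zero events in an arm of 106 does not measure them either, because it is the same however the question is worded.

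The conclusion assumes that sites use the question as the Adverse events section words it and that the unseen CRFs do not already go further. If CRF 5 already asks about worsening and CRF 6 or CRF 7 already carries an AE item, only the protocol text needs correcting.

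**What to change.** Three changes to data collection, none of which touches clinical management:

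1. In the Adverse events section and on CRF 5, ask about *any new symptom or condition, or worsening of an existing one*.
2. In the Visit 14 description, have the blinded assessor ask the same question, covering the time since Visit 13 and before the participant or assessor learns the allocation. Enter the answers on the AE Log that Table 2 already schedules for that visit.
3. Reconcile the Adverse events section, the Visits 3-13 and Visit 14 descriptions and the Case Report Forms list with Table 2, so that all of them show the same AE enquiry at the same visits.

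The cost is a few sentences of protocol text and a line on CRF 5, with no added visit or staff. More non-serious AEs will need to be logged. The change does not blind the enquiry during treatment, which remains with the researcher who delivers the intervention.
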